After consenting to participate in this study, a full demographic profile, known drug allergies or intolerances, and review of the subject's medical/surgical history will be recorded. Patients with known cardiac shunts will be excluded from the study. If the subject is a woman of childbearing potential, she will have a urine pregnancy test (the results of which will be made available to the subject prior to study initiation).

Whenever a subject undergoes a cardiac catheterization as part of their standard clinical care and agrees to participate in the study, we will perform the corresponding SHAPE measurements during the catheterization procedures to synchronously acquire SHAPE measurements and catheter based pressure measurements. Administration of Sonazoid will be performed under direct supervision of a medical doctor. Additionally, resuscitation equipment will be in immediate proximity to the patient during Sonazoid infusion. Three vials (6 ml) of Sonazoid microbubbles (16  $\mu$ l per vial when reconstituted) will be prepared for each subject by resuspending each vial in 2 ml of water for injection, supplied by GEHC, as described in the instructions provided by GEHC. Infusions will be performed as described. All materials and supplies used for the infusion procedure will be identical to those described in GE Healthcare's current Sonazoid IND. Briefly, an intravenous cannula will be placed in a vein in the subject's arm. A 0.9% NaCl solution will be started and used to fill up the connecting tubes before being connected to a 3-way stopcock. The

stopcock will then be connected to the extension tubing leading to the cannula. All three vials of suspended Sonazoid will be drawn into a 10 ml syringe, placed in a syringe pump at the same level or below the patient, and connected directly to the stopcock. After the stopcock to the 0.9% NaCl solution has been opened, the saline solution will be infused at a rate of at least 2 ml/min. Then, Sonazoid will be co-infused at the target rate of 0.024  $\mu$ l/kg body weight/minute (suspension infusion rate of 0.18 ml/kg/hour), but the rate may be reduced if necessary to achieve optimal levels of contrast. This infusion rate was selected based on our group's previous experiences with Sonazoid infusion in human subjects in general [Halpern et al. 2002; Landmark et al. 2008] and in SHAPE portal hypertension subjects in particular [Eisenbrey et al. 2013]. This dosing scheme is designed to avoid (or limit) the number of cases that has to be discarded due to insignificant enhancement (as in our pilot study; Eisenbrey et al. 2013). The dosage is based off the GEHC provided, study specific resuspension and infusion instructions and the total Sonazoid dose given over a maximum of 15 minutes (0.36  $\mu$ l/kg) will be well below the maximal tested dose which was still found safe in Phase I clinical trials (2.7  $\mu$ l of microbubbles/kg in PBI 0001 as detailed in the Sonazoid Investigator's Brochure). The duration of contrast agent infusion will range from 5 to 10 minutes.

Initially, ultrasound imaging will be performed with the SA 4-2 phased array to locate the tip of the Swan-Ganz catheter as it progresses through the cardiac chambers and guide the spectral Doppler sample volume placement (for SHAPE measurements). At this time, peripheral pressures will be acquired using a SphygmoCor system (in about 10 s). Based on the measured peripheral pressures, the SphygmoCor system will estimate the central aortic pressures (in another 10 s). This pressure value will be recorded and entered into the SHAPE software. Then the Sonazoid infusion will be initiated (dosage as indicated above) and once a constant concentration of contrast has been reached, the SHAPE algorithm to select the optimal incident acoustic pressure will be activated [Dave et al. 2013]. Ultrasound scanning will be first performed in the aorta. After the optimal incident acoustic pressure is determined, the data from the aorta will be obtained using the optimum incident acoustic pressure. Based on the aortic pressure (in mmHg, obtained from the SphygmoCor system) entered into the SHAPE software, and the acquired ultrasound data from the aorta (in dB), the SHAPE software will compute a calibration factor for each subject in units of mmHg/dB. The field of view will then be adjusted to acquire the data from the left or right ventricles. For each chamber, subsequent SHAPE data will be acquired simultaneously with the Swan-Ganz catheter data (as part of the patient's standard-of-care) using the optimal incident acoustic pressure. During the data acquisition from the right and left ventricles, the SHAPE software will use the calibration factor (in mmHg/dB) obtained from the aorta, to translate the subharmonic amplitude (in dB) to pressure values (in mmHg) and display these pressure values in real-time. Ultrasound data will be acquired from the left and right ventricles in 10 s segments. These measurements will be repeated as mentioned before. All the pressure values obtained using the SHAPE software will be stored on the SonixTablet. After acquiring the ultrasound imaging data the remainder of the heart catheterization will be completed by the attending cardiologist according to the patients' standard of care.

The proposed agent for the study, Sonazoid (GE Healthcare,), is a sterile non-pyrogenic suspension of lipid stabilized perfluorobutane microbubbles for contrast-enhancement, with a median diameter between 2.4 and 3.5  $\mu$ m [Forsberg et al. 2008]. Previous in vitro results have shown Sonazoid to be superior for SHAPE measurements relative to other ultrasound contrast agents [Halldorsdottir et al. 2011]. It should be pointed out that the safety of Sonazoid has already been established in numerous animal studies and in human studies for the evaluation of the liver and heart both in this country and in Europe [Landmark et al. 2008]. Sonazoid has been approved for use in patients with liver lesions in Japan (for more than 8 years) and it has since been approved for imaging use in South Korea, Taiwan, China and Norway [Bouakaz et al. 2007; Jang et al. 2013]. Finally, we have previously obtained investigator initiated IND (investigational new drug) for Sonazoid use in patients in USA and no adverse events were reported in this study no

adverse reactions attributable to contrast agent infusions were observed in our pilot study [Eisenbrey et al. 2013].

All examinations will be recorded. During the examination, the subharmonic pressure estimates will be displayed on the SonixTablet scanner, these estimates will be noted down and the data will be stored on a PC. Data will be compared to the catheter based measurements. Emergency services (e.g., a crash cart) will be available within the hospital in case of any acute adverse reactions. Patients will be monitored for a minimum of one hour post Sonazoid administration. During this time a trained CPR personnel and resuscitation equipment will be available. SHAPE data will later be compared to all clinical variables obtained from the patient to determine potential correlations.

**Statistical Methodology:** This is a study to prove the feasibility of real-time, in vivo SHAPE in human cardiac applications. Our statistical analysis will address the following major questions:

1. For the human studies, do subharmonic pressure estimates correlate (i.e.,  $r > 0.8$ ) with invasively-determined blood pressure measurements in patients scheduled for a left and/or right heart catheterization and will the errors in pressure measurements for clinically important ventricular systolic and diastolic pressures obtained using SHAPE be within 5 mmHg of the catheter-based pressure data (i.e., is real-time clinical SHAPE feasible)?
2. Will SHAPE measurements accurately predict other pressure contour-derived indices i.e., ventricular relaxation rate (peak isovolumic  $-dP/dt$ ) and relaxation time constant ( $\tau$  or  $\tau$ ) with errors less than 5%?

All of the statistical analyses proposed for the human clinical trial will be repeated split by racial and ethnic groups to determine if clinically important race/ethnicity differences exist in the ability of SHAPE to monitor cardiac pressures. All analyses and computations will be performed using IBM SPSS Statistics.

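### The feasibility conclusion rests only on readings that SHAPE produced, and no planned analysis counts the patients or ventricles in which it produced none

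*Combined protocol and SAP*

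**What the plan says.** The Statistical Methodology states the purpose: "This is a study to prove the feasibility of real-time, in vivo SHAPE in human cardiac applications". Question 1 then gives feasibility its content. One part is a correlation above 0.8 with the invasive pressures. The other is that the errors in ventricular systolic and diastolic pressures "obtained using SHAPE be within 5 mmHg of the catheter-based pressure data (i.e., is real-time clinical SHAPE feasible".

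The infusion paragraph of Trial Procedures, in giving the reason for the infusion rate, says: "This dosing scheme is designed to avoid (or limit) the number of cases that has to be discarded due to insignificant enhancement". It adds that such losses occurred in the group's pilot study. The Key References show that this pilot concerned the hepatic venous pressure gradient.

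Several acquisition steps in Trial Procedures need an adequate signal:

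- After infusion starts, "once a constant concentration of contrast has been reached, the SHAPE algorithm to select the optimal incident acoustic pressure will be activated".
- From the aortic signal and the SphygmoCor value, "the SHAPE software will compute a calibration factor for each subject in units of mmHg/dB".
- Then "Ultrasound data will be acquired from the left and right ventricles in 10 s segments", and these measurements are repeated.

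On recording, all examinations are kept; for the displayed estimates, "these estimates will be noted down and the data will be stored on a PC". All analyses are to be repeated by racial and ethnic group, to see whether clinically important "differences exist in the ability of SHAPE to monitor cardiac pressures".

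**The concern.** Whether a measurement method is feasible involves two questions: how often it gives a reading, and how good the reading is. Question 1 addresses only the second. A patient or ventricle without a usable SHAPE value has no pair with the catheter, so it enters neither r nor the error and drops out without trace.

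This is more than a missing detail of reporting. Followed as written, the rule gives the same answer whether SHAPE worked in every patient or in a modest fraction of them. Readers would learn how well SHAPE agrees with the catheter when it works, but not in what share of attempts it works. The repeats by race and ethnicity have the same gap: a group in which SHAPE more often gave no reading would not show up as different.

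**Working it through.** **Plan's own figure.** There is none to reproduce. The documents give no failure rate for the pilot or for this trial, no definition of a usable reading or analysis set, and no derivation of the sample size. The only number available is the maximum of 80 patients (Trial Population).

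**Where readings can be lost, and whether the plan counts the loss.**

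| Step in Trial Procedures | Possible failure | Counted in the planned analyses? |
|---|---|---|
| Ultrasound imaging before infusion | No adequate view | No |
| SphygmoCor aortic pressure, before infusion | No value to calibrate with | No |
| Constant contrast, choice of acoustic pressure | Insufficient enhancement | No |
| Aortic calibration | No mmHg/dB factor, so no ventricular pressure | No |
| Ventricular 10 s segments | One ventricle, or some segments, unusable | No |

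**What the planned criteria would show.** Inputs: n = 80 attempted (the planned maximum), failure counts x assumed, and one independent pair per patient assumed for r.

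- Usable proportion = (80 − x)/80. With u = 80 − x usable, the exact (Clopper-Pearson) limits are the 2.5% quantile of Beta(u, 80 − u + 1) and the 97.5% quantile of Beta(u + 1, 80 − u).
- 95% CI for an observed r of 0.8 = tanh(atanh 0.8 ± 1.96/√(u − 3)).

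| Failures (assumed) | Usable | Usable proportion (exact 95% CI) | 95% CI for r = 0.8 |
|---|---|---|---|
| 0 | 80 | 100% (95.5 to 100%) | 0.704 to 0.867 |
| 4 | 76 | 95% (87.7 to 98.6%) | 0.701 to 0.869 |
| 8 | 72 | 90% (81.2 to 95.6%) | 0.698 to 0.870 |
| 20 | 60 | 75% (64.1 to 84.0%) | 0.685 to 0.876 |

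For u = 60: atanh 0.8 = 1.0986 and 1.96/√57 = 0.2596, so the limits are tanh(0.8390) = 0.685 and tanh(1.3582) = 0.876.

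The usable proportion falls by 25 percentage points from the first row to the last, while the interval for r hardly moves. The planned results would not reveal the loss through their precision.

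**By ventricle.** Patients have left and/or right catheterization, so fewer than 80 may be attempted per ventricle. With 40 attempted (assumed) and no failures, the exact upper 95% limit for the failure proportion is 8.8%, against 4.5% for 0 of 80.

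**The case against.** The strongest reply is that the plan defines feasibility for itself, as correlation and error, and the primary objectives say the same. The sentence about discarded cases justifies an infusion rate chosen to prevent them; it does not say that cases in this trial will be discarded, and no exclusion rule is written. The losses it recalls came from a hepatic study. The requirement of constant contrast and the aortic calibration come before any ventricular acquisition and may expose a general failure of enhancement.

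Part of this stands. Exclusion is an inference, although a short one: the plan speaks of discarding, and neither criterion can be computed without a SHAPE value. The rate may be zero. It is also right that a compulsory limit on the failure proportion would add a third criterion, stricter in form than the plan's own two, which carry no confidence-limit rule.

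The rest does not remove the gap. The steps before acquisition are not a written rule for what counts as usable. They do not cover failure in one ventricle or in some segments, and patients lost at those steps would go uncounted too.

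Three stronger readings are tempting:

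- A reader might infer that r and the errors will be biased because poor cases are dropped. Nothing in the documents suggests that discards would depend on agreement with the catheter.
- A reader might infer that many cases will be lost, as in the pilot. No pilot rate is given, and the pilot was not cardiac.
- A reader might turn the table into a success rate, such as 60 of 80 patients within 5 mmHg. Question 1 does not say whether the 5 mmHg criterion applies per patient, to a mean error or to every pressure, so that step is not supported.

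**Conclusion.** The concern holds as a gap in what the feasibility conclusion covers. As written, the plan can declare real-time clinical SHAPE feasible without regard to the share of attempts that gave no usable reading, although it foresees such cases.

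The size is unknown. On assumed counts of 4 to 20 failures among 80, the share with a usable reading runs from 95% down to 75%, and the planned criteria would not distinguish these. Only the 80 comes from the documents. If there are no failures, reporting 0 of 80 (upper 95% limit 4.5%) would strengthen the claim. The plan should be changed, but no flaw in r or in the errors among evaluable readings is shown.

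**What to change.** Add to question 1 of the Statistical Methodology:

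> Among all enrolled patients in whom SHAPE was attempted (including those not infused because imaging or the SphygmoCor value could not be obtained), the number and proportion with no usable SHAPE reading is reported with an exact 95% CI and reasons: per ventricle attempted, and per patient (no usable reading in any attempted ventricle). Failed aortic calibration counts as a failure for every ventricle attempted. Missing catheter data, and infusions stopped for reasons unrelated to SHAPE, are listed separately and left out of both numerator and denominator. The feasibility conclusion is stated together with this proportion, and r and the errors are described as applying to evaluable readings only. The same counts are given by racial and ethnic group.

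Set the criterion for a usable reading in advance, including how the repeated 10 s segments combine for a ventricle, and apply it without reference to the catheter values. A pass/fail limit on the failure proportion is optional and for the team to decide.

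Cost: no extra patients. The work is to write the criterion, review the stored data and add one short table. The amount of review cannot be stated, because the number of segments is not given. The documents also do not say whether the stored data keep the subharmonic amplitude; if they do not, usability would have to be noted at acquisition. The headline may be less favourable, and the by-ventricle intervals will be wide.

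### The aortic pressure that calibrates SHAPE is read before the infusion but paired with a later aortic signal, so a pressure change in between can put a proportional, subject-specific error into the ventricular readings

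*Combined protocol and SAP*

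**What the plan says.** The sequence is in the combined protocol and SAP, Proposed Research Plan, under Trial Procedures.

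- **Reference pressure.** During the opening imaging step, while the catheter tip is being located: "At this time, peripheral pressures will be acquired using a SphygmoCor system (in about 10 s"). From that reading, "the SphygmoCor system will estimate the central aortic pressures (in another 10 s"). Next: "This pressure value will be recorded and entered into the SHAPE software".
- **Infusion.** "Then the Sonazoid infusion will be initiated (dosage as indicated above) and once a constant concentration of contrast has been reached", the optimisation of acoustic output is run.
- **Aortic signal.** "After the optimal incident acoustic pressure is determined, the data from the aorta will be obtained using the optimum incident acoustic pressure".
- **Factor.** From the pressure already entered and this aortic signal, "the SHAPE software will compute a calibration factor for each subject in units of mmHg/dB".
- **Use.** In both ventricles "the SHAPE software will use the calibration factor (in mmHg/dB) obtained from the aorta, to translate the subharmonic amplitude (in dB) to pressure values".
- **Comparator.** For each chamber, "subsequent SHAPE data will be acquired simultaneously with the Swan-Ganz catheter data".

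The Statistical Methodology section sets the criteria: ventricular systolic and diastolic errors within 5 mmHg of the catheter, and errors under 5% for peak -dP/dt and tau.

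**The concern.** The numerator of the factor (mmHg) and its denominator (dB) describe the aorta at two different times. Between them come the infusion start, the wait for steady contrast and the acoustic optimisation, in a patient undergoing catheterization. If aortic pressure changes over that interval, the factor is wrong for that subject and the error carries into the ventricular readings converted with it.

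Simultaneous catheter readings in the ventricles do not correct this, because the factor is already set. Averaging over 10 s segments or repeats does not remove it either, because the same factor is used throughout. The error would count against the 5 mmHg and 5% criteria as SHAPE inaccuracy. No planned measurement would show afterwards how much of it came from the sampling order.

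**Working it through.** The documents give no figure for the delay, the drift or the calibration error, so there is nothing to reproduce. The check is the order of events, followed by error propagation under the calibration forms that the text allows.

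**Inputs from the documents:** the order above; one factor per subject in mmHg/dB; limits of 5 mmHg and 5%; about 10 s plus another 10 s for a SphygmoCor estimate; infusion lasting 5 to 10 minutes; up to 80 subjects.

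**Assumptions (not in the documents):** aortic systolic 120 mmHg (range 100 to 140); LV systolic equal to aortic systolic; LV end-diastolic 15, right ventricular (RV) systolic 30 and RV diastolic 5 mmHg; pulse pressure 40 mmHg; drift 2 to 15 mmHg.

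**Step 1, interval.** Only the order is given. The stated infusion length bounds the part after infusion start. Nothing bounds the time from the cuff reading to infusion start.

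**Step 2, simple ratio.** Let k = P_ref / S_aorta. If P_ref differs by d from the aortic pressure P_ao at the time of the scan, k is wrong by the fraction d / P_ao, and a ventricular pressure P is wrong by P × d / P_ao. At P_ao = 120 mmHg:

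| Drift d (mmHg) | Factor error | LV systolic | LV end-diastolic | RV systolic | RV diastolic |
|---|---|---|---|---|---|
| 5 | 4.2% | 5.0 | 0.6 | 1.25 | 0.2 |
| 10 | 8.3% | 10.0 | 1.25 | 2.5 | 0.4 |
| 15 | 12.5% | 15.0 | 1.9 | 3.75 | 0.6 |

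Over aortic systolic 100 to 140 mmHg, a 15 mmHg drift gives an RV systolic error of 3.2 to 4.5 mmHg and a diastolic error of at most 2.25 mmHg. Peak -dP/dt carries the same percentage error as the factor, so its 5% limit is reached at d = 0.05 × P_ao, which is 5, 6 or 7 mmHg for P_ao of 100, 120 or 140. Tau is unchanged because rescaling only shifts log pressure: a simulated decay with tau 0.045 s returns 0.045 s after a 5% or 10% factor error.

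**Step 3, slope from pulse pressure.** The factor error is the change in pulse pressure divided by 40, so 2, 4 or 6 mmHg gives 5%, 10% or 15%.

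| Pulse-pressure change (mmHg) | Whole reading scaled: LV systolic 120 | Whole reading scaled: diastolic 10 | Anchored at 80: LV systolic 120 | Anchored at 80: diastolic 10 |
|---|---|---|---|---|
| 2 | 6 | 0.5 | 2 | 3.5 |
| 4 | 12 | 1.0 | 4 | 7.0 |
| 6 | 18 | 1.5 | 6 | 10.5 |

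The scaled columns are P × error. The anchored columns are |P − 80| × error, for example (120 − 80) × 5% = 2 and (80 − 10) × 5% = 3.5. In both variants the 5% limit on -dP/dt is used up by a 2 mmHg change in pulse pressure. A parallel shift, such as 120/80 to 130/90, leaves pulse pressure at 40 and the slope unchanged. If readings were also anchored to the early SphygmoCor value, a parallel shift would enter through the anchor.

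**Step 4, spread across subjects.** Under the ratio form the LV systolic error equals d. If d is normal with mean zero, the share of subjects beyond 5 mmHg from drift alone is 2 × (1 − Φ(5/SD)): about 10%, 32% and 53% for assumed SDs of 3, 5 and 8 mmHg.

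**The case against.** The strongest case against is that only the order is certain. Interval, drift size, drift direction and calibration formula are all absent, and the consequences differ widely between forms. That stands, and it rules out several stronger readings that a reader might infer:

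- **That the aortic signal comes minutes later.** No interval is stated.
- **That every ventricular pressure carries a fixed mmHg error.** A mmHg/dB factor gives a constant percentage. Under a ratio, low pressures are barely affected and tau not at all. A constant mmHg error would need an offset or anchor, which the text does not describe.
- **That any drift matters.** A pulse-pressure slope without an anchor is unaffected by a parallel shift.
- **That calibration is definitely never repeated.** The section has a sentence about repeating measurements. It follows the ventricular segments and does not mention calibration, so the most that can be said is that no repeat is described.
- **That the trial would wrongly reject feasibility.** Drift of unknown sign adds scatter and may offset other errors. It biases the mean only if it is systematic, which nothing in the documents shows.

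It can also be argued that this sequence is the procedure under test, so its timing error is part of the method's accuracy. That is fair for performance as delivered. But without a second reading the trial could not say whether a miss came from SHAPE or from the order of sampling.

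**Conclusion.** The point holds in limited form. The plan calibrates each subject with a pre-infusion pressure and a post-infusion aortic signal, and describes nothing that detects or corrects a change between them. The result can be a proportional error specific to the subject, which repeats within that subject do not remove.

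It can be material for LV systolic pressure and -dP/dt. Under a ratio at an assumed 120 mmHg, drifts of 5 and 6 mmHg respectively use up the limits. Under a pulse-pressure slope at an assumed 40 mmHg, a 2 mmHg change uses up the -dP/dt limit. Under the ratio form it is minor for diastolic and right-sided pressures and nil for tau. Only a slope anchored near aortic diastolic pressure would make the low pressures vulnerable.

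Across subjects the expected effect is mainly extra scatter. All pressures and drifts used here are assumptions. The order of events and the two limits come from the documents.

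**What to change.** In the calibration sequence under Trial Procedures:

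1. Take the SphygmoCor reading used for calibration during, or immediately next to, the aortic SHAPE acquisition, once contrast is steady and acoustic output has been optimised. Compute the factor from that reading.
2. Keep the pre-infusion reading. Timestamp both readings and the aortic acquisition, and report the distribution of the change between readings.
3. State how the factor is computed: ratio or pulse-pressure slope, and whether there is an offset or anchor.

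The cost is about 20 s (10 s to acquire plus 10 s to estimate) with a device the trial already uses, and one more cuff inflation. Out of a 5 to 10 minute infusion, 20 s is 20/600 = 3.3% to 20/300 = 6.7% of the window. The change removes the timing part of the calibration error at the aortic acquisition. SphygmoCor's own estimation error remains.

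### One pre-infusion SphygmoCor value is the only mmHg reference for each patient's SHAPE calibration; its random error cannot average out and may by itself breach 5 mmHg for LV systolic pressure

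*Combined protocol and SAP*

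**What the plan says.** Under Trial Procedures, the peripheral reading takes about 10 s, after which "the SphygmoCor system will estimate the central aortic pressures (in another 10 s"). Of the result, the plan says "This pressure value will be recorded and entered into the SHAPE software". The wording is singular. It does not say whether the value is systolic, diastolic or mean.

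The order of events is then: "Then the Sonazoid infusion will be initiated (dosage as indicated above) and once a constant concentration of contrast has been reached", the acoustic output is optimised, and the aorta is scanned. From the SphygmoCor pressure and the aortic amplitude, "the SHAPE software will compute a calibration factor for each subject in units of mmHg/dB". The same factor serves both chambers: "the SHAPE software will use the calibration factor (in mmHg/dB) obtained from the aorta, to translate the subharmonic amplitude (in dB) to pressure values".

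Ventricular data are collected in 10 s segments, followed by "These measurements will be repeated as mentioned before". Nothing earlier says what is repeated or how often, and the sentence's position ties it to the ventricular segments.

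The plan mentions no replicate SphygmoCor readings, no averaging, no repeatability figure and no check of the entered value against a catheter aortic pressure.

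Statistical Methodology, question 1, asks whether errors for ventricular systolic and diastolic pressures "obtained using SHAPE be within 5 mmHg of the catheter-based pressure data". It does not say whether the limit applies to each reading, each patient or the mean error.

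**The concern.** The scale of every SHAPE pressure in a patient is tied to one short cuff-based estimate. If that reading is off by chance, the patient's factor is off, and so are all the ventricular values derived from it. More ventricular segments give a more precise average of values that share the same error. This happens even when the true pressure does not change between the reading and the scan.

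At stake is the 5 mmHg criterion. Reading noise widens the SHAPE-minus-catheter differences, most of all where pressure is highest. With one stored reading per patient, there is also no direct estimate of how much of the observed error comes from the SphygmoCor step rather than from the subharmonic signal.

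**Working it through.** The plan has no error budget or sample-size calculation, so there is no stated figure to reproduce.

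**Inputs from the documents:** limit 5 mmHg; up to 80 patients; one factor per subject in mmHg/dB; about 10 s for the reading and 10 s for the central estimate.

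**Assumptions, not in the documents:** SD of one reading, s = 2, 3, 5 or 8 mmHg; normal errors; aortic systolic 120, LV systolic 120, RV systolic 25, LV end-diastolic 10 to 25, RV diastolic 5 mmHg; the factor is one pressure divided by one amplitude, with no offset.

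**Step 1: how the error carries over.** With a gain-only factor, an error e in the aortic value gives a ventricular error of (ventricular pressure / aortic pressure) × e. For LV systolic pressure this is (120/120) × e = e.

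**Step 2: threshold.** With no other error source, 95% of patients stay within 5 mmHg only if s ≤ 5/1.96 = 2.55 mmHg.

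**Step 3: LV systolic, limit read per patient.** The share beyond 5 mmHg is 2[1 − Φ(5/s)]. For the mean of three independent readings, replace s by s/√3, a reduction of 1 − 1/√3 = 42%.

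| Reading SD (mmHg) | One reading | Mean of three |
|---|---|---|
| 2 | 1.2% | <0.1% |
| 3 | 9.6% | 0.4% |
| 5 | 32% | 8.3% |
| 8 | 53% | 28% |

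**Step 4: lower pressures, gain only, s = 5.**

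| Pressure (mmHg) | Error SD (mmHg) | Reading error needed to reach 5 mmHg |
|---|---|---|
| RV systolic 25 | 5 × 25/120 = 1.04 | 24 |
| LV end-diastolic 25 | 1.04 | 24 |
| LV end-diastolic 10 | 0.42 | 60 |
| RV diastolic 5 | 0.21 | 120 |

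If the value also set an offset, the error would pass one-to-one at every pressure and the Step 3 figures would apply throughout.

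**Step 5: limit read as mean error over 80 patients.** The LV systolic standard error from reading noise is s/√80: 3/8.94 = 0.34, 5/8.94 = 0.56 and 8/8.94 = 0.89 mmHg.

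**Step 6: sensitivity to how the factor is formed.** If the entered value were a mean pressure (93 mmHg assumed), the LV systolic multiplier would be 120/93 = 1.29, and s = 3 would put 19.6% of patients beyond 5 mmHg. If the gain came from an assumed aortic pulse pressure of 40 mmHg, with independent errors of SD 5 in systolic and diastolic, its relative SD would be √2 × 5/40 = 0.177. That is an error SD of 19.4 mmHg over a 110 mmHg LV excursion and 3.5 mmHg over a 20 mmHg RV excursion. The plan speaks of one value, so Steps 1 to 4 use the single ratio.

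**The case against.** The strongest reply is that the problem is narrow and its size is not known from the documents. Most of that reply stands.

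- A reader might infer that the reading's error enters every SHAPE pressure at full size. The documents do not support this. They describe a factor in mmHg/dB and no offset step, and Step 4 shows the effect is then small for RV and diastolic pressures.
- A reader might infer that the SphygmoCor value is the whole calibrator. It is not, because the aortic amplitude is the other input. It is the only mmHg reference.
- No repeatability SD is given. At 2 mmHg only 1.2% of patients exceed the limit, and averaging has little to gain.
- The per-patient reading of the limit is one possibility among several. On a mean-error reading, random noise nearly cancels.
- SphygmoCor calibration is part of how SHAPE produces a pressure, so its noise belongs to the error being tested. A failure caused by it would be a real failure of the method as specified.
- It would be too strong to say that the cause could not be identified afterwards. A shared gain error would appear as a common within-patient scale discrepancy against the simultaneous catheter data. Other gain errors look the same, however, so attribution would be incomplete.
- A single reading is inferred from singular wording and silence on replicates. Repeats are not ruled out.

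What the reply does not remove is that no stated step averages the reading's error, and that LV systolic pressure is named in the second objective and falls within the ventricular pressures of question 1.

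**Conclusion.** The point holds for LV systolic pressure and is conditional on the reading SD. The plan specifies one pre-infusion SphygmoCor value as the sole mmHg reference for each patient, so its random error is common to all that patient's SHAPE values and is not reduced by repeating ventricular segments. If the limit is applied per patient and the factor is a single-ratio gain, a reading SD above about 2.6 mmHg by itself puts more than 5% of patients beyond 5 mmHg for LV systolic pressure.

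The documents do not support extending this to all ventricular pressures, or treating it as a certain cause of failure. Both would need information the plan does not give: an offset in the calibration, a repeatability figure, and a per-patient definition of the limit. This is a worthwhile low-cost improvement and not a flaw that invalidates the design.

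**What to change.** In Trial Procedures, replace the single SphygmoCor step with three acquisitions before the infusion. Enter their mean into the SHAPE software and store all three values. In Statistical Methodology, add that the within-patient SD of the three readings will be reported next to the SHAPE error. Pool it across patients, because one patient's three readings give only 2 degrees of freedom. In the same edit, state which pressure is entered and whether the factor is a gain alone or a gain plus an offset, since this decides which ventricular pressures are affected.

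Cost: two further readings at about 20 s each by the plan's own timings, so about 40 s plus any interval between readings. All of it falls before contrast starts and needs no new device or staff.

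Limits: the 42% reduction in random SD is the most that three readings can give and requires independent errors. Consecutive readings may share error from cuff placement and from the central-pressure estimation. Systematic SphygmoCor bias and any drift between the reading and the aortic scan also remain.
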